#### 4.2.6 Pharmacokinetics

Serum MEDI3506 concentrations will be summarised using descriptive statistics at each visit by study intervention group and will be listed for each participant from the PK population. Geometric mean (together with CV%) serum MEDI3506 concentration over time will be plotted. Individual serum MEDI3506 concentration over time plots will be provided.

Serum MEDI3506 concentrations by ADA category (TE-ADA negative, TE-ADA positive, ADA negative) will be summarised using descriptive statistics at each visit by study intervention group for the PK population. Spaghetti plots of individual serum MEDI3506 concentrations over time by ADA category (non TE-ADA positive, TE-ADA positive, ADA negative) will be provided.

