# 7 DISCONTINUATION OF STUDY INTERVENTION AND PARTICIPANT DISCONTINUATION/WITHDRAWAL

# 7.1 Discontinuation of Study Intervention

The PI may determine it necessary on medical grounds for a participant to permanently discontinue (definitive discontinuation) study intervention. Note that discontinuation from study intervention is NOT the same thing as withdrawal from the study.

If study intervention is permanently discontinued, the participant will remain in the study and attend all remaining intervention period and follow-up period visits.

See the SoA (Section 1.3) for data to be collected at the time of discontinuation of study intervention and follow-up and for any further evaluations that need to be completed.

An individual participant will not receive any further study intervention if any of the following occur in the participant in question:

AstraZeneca

- 1 Withdrawal of consent to further treatment with study intervention.
- 2 Lost to follow-up.
- 3 Any anaphylactic reaction to study intervention requiring epinephrine administration.
- 4 Any treatment-emergent AE that is Grade  $\geq 4$  in severity (see Appendix B).
- 5 Any treatment-emergent SAE that is in the cardiac disorders system organ class, except atrial arrhythmias.
- Confirmed diagnosis of new onset of heart failure during the study (except for transient heart failure secondary to atrial arrhythmia). For a participant with suspected new onset of heart failure, the participant should not be administered study intervention unless and until the diagnosis is refuted. Study intervention should also be temporarily withheld during any episode of transient heart failure secondary to atrial arrhythmia.
- Any other AE that, in the opinion of the investigator or the sponsor, warrants discontinuation of further dosing of study intervention.
- 8 Pregnancy.
- 9 Following randomization, the participant mee\* > 1 the exclusion criteria or fails to meet all of the inclusion criteria for study par cipe tion.
- 10 Any AECOPD with duration > 14 days.
- 11 The participant misses 2 consecutive doces.

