# 2 ANALYSIS SETS

# 2.1 Definition of analysis sets

The following populations are defined:

Table 6	Populations for	or analysis
	- optimitions is	, , , , , , , , , , , , , , , , , , , 

Population/Analysis set	Description
All Subjects/subjects enrolled	Participants who have signed the informed consent form during screening period. Participants who have been randomized will be analysed according to their randomized study intervention group.
All randomized subjects	Participants who are randomized. Participants will be analysed according to their randomized treatment group.
ITT population	Participants who are randomized and receive any study intervention. Participants will be analysed according to their randomized study intervention group.
As-treated Population	Participants who are randomized and receive any study intervention. Participants will be analysed according to the study intervention they actually receive.
PK population	Participants who received at least one dose of MEDI3506 and had at least one detectable serum concentration measurement post first dose of study

Population/Analysis set	Description
	intervention. A participant is considered as having at least one detectable serum concentration measurement post first dose if has at least one plasma concentration that is not below the LLOQ after the first dose. Participants will be analysed according to the study intervention they actually receive.
CCI	CCI

Table 6	Populations	for	analysis
1			

ITT = Intent to treat; PK = pharmacokinetic(s).

'All Subjects/subjects enrolled' population will be used to summarise all participants disposition. "All randomized subjects" will be used to summarise all randomized patients including the patient randomized but not treated. The ITT population will be used to summarise all demographic and baseline characteristics, concomitant medications, and efficacy measures.

The As-treated population will be used to summarise all safety measures (AEs, ADA, laboratory tests, ECG, and vital signs). The PK population will be used to summarise PK measures.

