# 3.1.4 Handling of missing data

No imputation for missing efficacy endpoints will be done. For the primary analysis, MMRM will be used and which, in the event of missing data, uses all data that are available.

Missing safety data will generally not be imputed. However, safety assessment values of the form of "< x" (below the lower limit of quantification) will be imputed as "0.5x LLOQ" in the calculation of summary statistics but displayed as "< x" in the listings. No imputation will be done for laboratory values of the form ">x" (above the upper limit of quantification) and the value ">x" will be displayed in the listings. Note that 0 should not be used as an imputed value in case the endpoint requires a log transformation.

In the different analyses performed, the log-transform eosinophil value can be used, a constant of 0.005 will be added to all the patients at the time of the calculation of the log eosinophil to avoid the issues due to the log-transformation.

Additionally, adverse events that have missing causality (after data querying) will be assumed to be related to study drug.

Missing ADA result at baseline data will be assumed to be negative, for other missing ADA data, no imputation is planned.

PK serum concentrations below the lower limit of quantification will be reported as NQ (Not Quantifiable) in the listings with the LLOQ defined in the footnotes of the relevant TFLs. Individual serum concentrations that are Not Reportable will be reported as NR and those that are missing will be reported as NS (No Sample) in the listings. PK serum concentrations that are NQ, NR or NS will be handled as follows for the provision of descriptive statistics:

- Any values reported as NR or NS will be excluded from the summary tables and corresponding figures.
- At a time point where less than or equal to 50% of the concentration values are NQ, all NQ values will be set to the LLOQ, and all descriptive statistics will be calculated accordingly.

- At a time point where more than 50% (but not all) of the values are NQ, the gmean, gmean  $\pm$  gSD and gCV% will be set to NR. The maximum value will be reported from the individual data, and the minimum and median will be set to NQ.
- If all concentrations are NQ at a time point, no descriptive statistics will be calculated for that time point. The gmean, minimum, median and maximum will be reported as NQ and the gCV% and gmean  $\pm$  gSD as NR.

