#### 3.1.5 Analysis visit windows

For the CCI COPDCompEx related analyses no analysis visit windows will be applied.

For PK related analyses no analysis visit windows will be applied and the actual visits/timepoints will be used instead.

Visit windows will be used for all scheduled assessments to allow for by-visit analyses, since not all assessments are performed on the scheduled day. Unless specified otherwise, all efficacy and safety analyses will be based on the analysis visit windows. The actual assessment day will be mapped to the planned study visit following the analysis visit windowing rules below:

- If more than one assessment falls within a visit window, the closest non-missing assessment to the scheduled day will be used in the analysis.
- If more than one non-missing assessment actual dates are equidistant from the target day, the earlier assessment will be used in the analysis.
- If screening and re-screening visits have same date and time then the re-screening assessment will be used in the analysis.

The visit windows will be calculated by bisecting the scheduled visit days. The lower limit of each window will be the mean of the 2 adjacent planned study days, rounded up to the nearest integer, except for the first post-treatment visit, which will start at 2. The upper limit of each window will be the mean of the 2 adjacent planned study days, rounded down to the nearest integer.

Protocol Visit	Week	Analysis Visit	Scheduled Study Day	Visit Window for Analysis (Days)
SV3	Week 0	Baseline	1	All assessments prior to the first administration of investigational product
SV5	Week 2	Visit 5, Week 2	15	All assessments on or after the first administration of investigational product to 22
SV6	Week 4	Visit 6, Week 4	29	23 to 43
SV7	Week 8	Visit 7, Week 8	57	44 to 71

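### By-visit serum MEDI3506 summaries set no condition on dosing status, so washout samples are pooled with on-dose troughs, mainly at Weeks 20, 24 and 28

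*SAP*

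**What the plan says.** - **Summary rule.** SAP 4.2.6: "Serum MEDI3506 concentrations will be summarised using descriptive statistics at each visit by study intervention group". The geometric mean with CV% is plotted over time, and the summary is repeated by ADA category. The outputs are Tables 14.2.2.4.1 and 14.2.2.4.2 and Figure 14.2.2.4.1. Neither 4.2.6 nor the output notes set a condition on doses received or time since last dose.
- **Population.** SAP 2.1 defines the PK population as "Participants who received at least one dose of MEDI3506 and had at least one detectable serum concentration measurement post first dose of study" intervention.
- **Values left out.** SAP 3.1.4: "Any values reported as NR or NS will be excluded from the summary tables and corresponding figures". Where no more than half the values at a time point are below quantification, "all NQ values will be set to the LLOQ, and all descriptive statistics will be calculated accordingly".
- **Visit label.** SAP 3.1.5: "For PK related analyses no analysis visit windows will be applied and the actual visits/timepoints will be used instead".
- **Attendance after stopping.** Protocol 7.1: "If study intervention is permanently discontinued, the participant will remain in the study" and will "attend all remaining intervention period and follow-up period visits". Treatment ends when "The participant misses 2 consecutive" doses, so a single missed dose does not end it.
- **Sampling.** Protocol Table 3 schedules PK at SV3, SV5, SV6, SV8 and SV10 to SV14.
- **Partial doses.** SAP 3.7 counts a visit at which only one syringe was given as a treatment interruption.

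**The concern.** A serum concentration depends directly on when the last dose was given and how many came before it. Under these rules, a sample labelled Week 28 may come from someone dosed 28 days earlier or from someone whose last dose was 112 days earlier, and both enter the same geometric mean. Off-dose concentrations lie below on-dose troughs, so the pull is always downward. The geometric mean is especially sensitive to a few very low values.

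The concentration-time profile is a secondary endpoint, and readers will take it to describe exposure on the regimen. The ADA-category table shares the weakness. If stopping were related to ADA status, a difference in dosing could look like an effect of ADA on exposure.

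Elsewhere the SAP does separate data by dosing status. COPDCompEx counts on-treatment events only (SAP 3.3.4), and FEV1 has a supportive analysis without visits after discontinuation (SAP 4.2.4.2). PK has neither.

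**Working it through.** **Inputs from the documents**
- Half-life: Protocol 5.3 equates 16 weeks with 5 half-lives, so 112 / 5 = 22.4 days.
- Dosing every 28 days at Weeks 0, 4, 8, 12, 16, 20 and 24 (seven doses). Samples are taken before dosing.
- 72 participants per arm are to be randomised.

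**Assumptions, not in the documents**
- First-order decay in one compartment, with doses adding up.
- Share p of sampled MEDI3506 participants who have stopped: 2% to 10%. With 72 in the arm, 10% is about 7 people and 2% is 1 or 2.

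**The plan's own figure.** The plan has no figure for this bias. Protocol 4.3 gives 21 µg/mL as a predicted average at steady state. Its monkey AUC of 28012 over 4 weeks gives 28012 / (21 × 28) = 47.6, close to the upper end of the stated 38- to 47-fold margin. The 21 µg/mL is thus an average over the dosing interval, not a trough.

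**Step 1: what an off-dose sample contains.** Over one 28-day interval the carried-over fraction is r = 2^(−28/22.4) = 0.420. At Week 28:
- All seven doses: r + r² + … + r⁷ = 0.724.
- Stopped after Dose 4 (Week 12): r⁴ + r⁵ + r⁶ + r⁷ = 0.0522. Ratio R = 0.0522 / 0.724 = 0.072.
- Stopped after Dose 3 (Week 8): r⁵ + r⁶ + r⁷ = 0.0210. R = 0.0210 / 0.724 = 0.029.

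Ratios to the fully dosed trough:

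| Dosing history | Week 20 | Week 24 | Week 28 |
|---|---|---|---|
| Stopped after Dose 3 | 0.17 | 0.07 | 0.03 |
| Stopped after Dose 4 | 0.41 | 0.17 | 0.07 |
| Missed Week 16 dose only | 0.41 | 0.75 | 0.90 |
| Missed Week 24 dose only | 1.00 | 1.00 | 0.42 |

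Adding first-order absorption at an assumed 0.3/day leaves these ratios essentially unchanged.

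**Step 2: effect on the geometric mean.** On the log scale the mean shifts by p × ln R, so the pooled geometric mean is R^p times the on-dose value. At Week 28:
- 2% stopped after Dose 4: 0.072^0.02 = 0.949, a fall of about 5%.
- 10% stopped after Dose 4: 0.072^0.10 = 0.769, a fall of about 23%.
- 10% stopped after Dose 3: 0.029^0.10 = 0.702, a fall of about 30%.

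For 10% stopped after Dose 4, a half-life of 16 days gives 0.69 and one of 28 days gives 0.81. The arithmetic mean moves less: 1 − 0.10 + 0.10 × 0.072 = 0.91.

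**Step 3: effect on spread.** Pooling adds p(1 − p)(ln R)² to the log variance. With 10% stopped after Dose 4 this is 0.09 × 6.91 = 0.622. If the true geometric CV were 30% or 40% (assumed), the log variances are 0.086 and 0.148. The pooled values are √(exp(0.708) − 1) and √(exp(0.770) − 1), or about 102% and 108%.

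**The case against.** **The outputs are descriptive, and the mixing would be visible.** No PK hypothesis is tested. Medians, minima and maxima are tabulated, individual profiles are plotted, and every administration is listed with its date and dose. A population PK model may also be fitted. This stands in part: a careful reader could find the problem. None of it corrects the summary table or the mean plot, and the population model is optional.

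**An all-samples summary is defensible.** It describes exposure in everyone treated, in keeping with the treatment-policy estimand for FEV1. Restricting to on-dose participants selects on something that happens after dosing starts. If low exposure or ADA leads to stopping, the restricted summary could overstate exposure. This stands, and it is why both versions are needed, above all by ADA category.

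**The size is unknown.** Participants who withdraw from the study give no later samples, and setting unquantifiable values to the LLOQ softens the pull somewhat. Visit skipping under Protocol 4.1.2 applies to crisis disruption, not routine conduct. This stands, and the percentages are illustrations.

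**A reader might infer that the trial would report missing its 20 to 21 µg/mL target.** The documents do not support that. The prediction is an average, while the Week 12, 20, 24 and 28 samples are pre-dose troughs. Under the same model with absorption at 0.3/day, a fully dosed trough is about 0.70 of the average, or 0.70 × 21 ≈ 14.7 µg/mL. It would lie below 20 with every off-dose sample removed. No passage plans to compare the table with that target.

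**Conclusion.** The point holds as a gap in the PK summary rules. Without a dosing-status condition, the by-visit geometric mean understates on-treatment trough exposure, and its CV% overstates variability, whenever participants who stopped or missed doses are still sampled. The direction follows from the design. The size does not: it runs from about 5% at Week 28 (2% stopped after Dose 4) to about 30% (10% stopped after Dose 3). That range rests on the 22.4-day half-life, a one-compartment model and assumed stopping rates.

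Weeks 20, 24 and 28 are the visits mainly affected. Week 12 is touched only by earlier stops or missed doses: a participant whose last dose was at Week 8 is still on schedule at the Week 12 sample. Weeks 32 and 36 are washout for everyone by design, but those who stopped early remain further down the curve.

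Nothing here touches the primary endpoint, alpha, power or sample size, and it does not show that the dose would appear to fail its exposure target. A bias in the ADA comparison is possible only if stopping differs by ADA status, on which the documents are silent.

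**What to change.** In SAP 4.2.6, and in the notes to Tables 14.2.2.4.1 and 14.2.2.4.2 and Figure 14.2.2.4.1, pre-specify an on-dose by-visit summary:

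- Include a sample only if all scheduled doses up to that visit were given in full and the sample falls within the visit window relative to the last dose.
- For SV13 and SV14, require all doses through SV11.
- Flag every other sample and list it with actual time since last dose.
- Keep the all-samples summary alongside, including by ADA category, and state that the on-dose version selects on a post-dose event.

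Requiring only the preceding dose is not enough. Someone who missed Week 16 but was dosed at Week 20 would qualify at Week 24 with about 0.75 of the on-schedule trough.

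The cost is SAP wording, one flag built from dosing dates and volumes already recorded, one extra table and slightly fewer observations per visit. The rule should be fixed before unblinding, because choosing afterwards which samples to set aside would be post hoc.

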#### 4.2.7 Immunogenicity

Summary of ADA responses during the study with number and percentage of participants in each category (defined in Section 3.6.2) will be provided by study intervention group. Summary of AEs by ADA status (TE-ADA positive, Non-TE-ADA positive, ADA negative, ADA persistently positive and TE-ADA positive with maximum titre > median of maximum titres) will be provided. ADA results will be listed, and a listing with key information on ADA positive participants will be provided.
If there is a high incidence of ADA, the association of ADA with MEDI3506 concentration will be assessed. In addition, the relationship between ADA and efficacy may be evaluated.

T.2.0	Exploratory chapolities	
4.2.8.1	CCI	
CCI		
CCI		
CCI		
4.2.8.2	CCI	
CCI		
CCI		
CCI		
CCI		
4.2.8.3	CCI	

# 4.2.8 Exploratory endpoints

Statistical Analysis Plan D9180C00002 - 2.0

CCI				
CCI				
CCI 4.2.8.4	CCI			
CCI				
CCI				
4.2.8.5 CCI	CCI			
CCI				
				E

Statistical Analysis Plan D9180C00002 - 2.0

CCI			
4.2.8.6			
4.2.8.7	CCI		
CCI			
	CCI		
4.2.8.8 CCI			
CCI			
CCI			
CCI			
1280	CCI		
4.2.8.9 CCI			
CCI			
CCI			
4.2.8.10	CCI		

CCI		
CCI		
CCI		
4.2.8.11 CCI CCI		
CCI		
CCI		
CCI		

4.2.8.12 CCI		
CCI		
CCI		
CCI		
CCI		

## 4.2.9 Exposure

Duration of exposure as calculated in Section 3.1.7.5 will be summarised by study intervention groups for the As-treated population.

Number and percentages of participants receiving:

- 1 or more doses;
- 2 or more doses;
- 3 or more doses;
- 4 or more doses;
- 5 or more doses;
- 6 or more doses;
- 7 doses

will be summarised by study intervention group for the As-treated population. Additionally, the number of doses received will be summarised using descriptive statistics of mean, median, upper and lower quartiles.

Number and percentage of participants who received initial dose, who had no interruption, who had any interruption or 1, 2, 3, etc. interruption will be summarised by study intervention group for the As-treated population.

Exposure details, such as duration of exposure, date of each treatment administration and dose per administration, will be listed for As-treated population.

## 4.2.10 Safety data

## 4.2.10.1 Adverse events

All AE summary tables and listings will be created by study intervention group for the Astreated population, unless otherwise specified. AEs occurred during study intervention and follow-up period (both periods are defined in section 3.1.7) will be reported in summary tables. All AEs, including AEs for enrolled but not randomized participants and for participants who were not exposed to treatment, will be listed.

Overview tables will contain number and percentages of participants and number of episodes in following categories:

- Any AEs
- Any AE with toxicity grade 4 or 5
- Any AEs with outcome = death
- Any SAEs (including events with outcome = death)
- Any AEs leading to discontinuation of IP
- Any AEs leading to dose interruption
- Any AEs leading to withdrawal from study
- Any AESI

Number and percentage of participants with at least one AE by SOC term will be produced by study intervention group.

Number and percentage of participants with AE by SOC and PT term will be summarised by study intervention group. Total number of AEs by SOC and PT term will be summarised by study intervention group.

The number and percentages of participants with AEs occurring in >5% of participants in Total study intervention group will be summarised by PT and study intervention group. Non-serious adverse events occurring in greater than 5% of participants (including number and percentages of participants and number of events) in any study intervention group by SOC and PT term will be summarised by study intervention group.

The number and percentages of participants with AEs by maximum reported toxicity grade by PT term will be summarised by study intervention group.

The number and percentages of participants with AEs by relationship as assessed by investigator will be summarised by PT term and study intervention group.

Number and percentage of participants with AE leading to dose interruption of IP by SOC and PT term will be summarised by study intervention group.

The number and percentages of participants with AEs with outcome of death by SOC and PT term will be summarised by study intervention group. Key participant information for participants experienced AEs with outcome of death will be produced for each study intervention group using following information:

- Study intervention group
- Participant identifier
- Sex
- Age (years)
- Event term as reported by the investigator
- PT term
- Time from first IP administration to onset of AE (days) as derived in Section 3.1.8.6
- Treatment period
- Time from last IP administration to death (days) as derived in Section 3.1.8.8
- Time from first IP administration to death (days) as derived in Section 3.1.8.9
- Received treatment for AE
- Reasonable possibility AE caused by IP

The number of SAEs by SOC and PT term will be summarised by study intervention group. The number and percentages of participants with SAEs by SOC and PT term will be summarised by study intervention group. Key participant information for participants experienced SAEs will be produced using following information:

- Study intervention group
- Participant identifier
- Sex
- Age (years)
- Event term as reported by the investigator
- PT term
- Time from first IP administration to onset of AE (days) as derived in Section 3.1.8.6

- Time from last IP administration prior to AE start date, calculated for AEs starting after the discontinuation of the IP.
- Time from start of IP administration to becoming serious
- Outcome
- Action taken with IP
- Reasonable AE caused by IP

The number and percentages of participants with AEs leading to discontinuation of investigational product by SOC and PT term will be summarised by study intervention group. Key participant information for participants experienced AEs leading to discontinuation of IP will be produced using following information:

- Study intervention group
- Participant identifier
- Sex
- Age
- AE as reported by the investigator
- PT term
- Time from first IP administration to AE onset
- Time from first IP administration to discontinuation of IP
- Seriousness
- Outcome
- Reasonable possibility AE caused by IP

Number and percentage of participants with AE of special interest by maximum reported toxicity grade will be summarised by study intervention group. A list of PT terms for AEs of special interest will be produced. Number of participants with AE for each medical concept (injection site reaction (ISR), serious hypersensitivity, serious infection, progression of heart failure, gastrointestinal adverse reactions, COVID-19) by maximum reported toxicity grade will be summarised by study intervention group.

Number of subjects with COVID-19 related AEs of special interest by SOC and PT will be summarised by treatment group and for total MEDI3506. Similar table will be repeated for the number of subjects with COVID-19 related serious AEs of special interest.

All AEs will be listed as well as AEs among ADA positive participants.

